RATIONALE	
There is a lack of understanding regarding the mechanisms that cause concussive signs and symptoms, and there is no definitive consensus on how to best evaluate or treat an individual with concussion. As a result, it is difficult to evaluate when it is necessary for an athlete to be removed from play after a possible head injury. Current sideline assessments may be subject to the athlete's lack of effort during baseline testing, leading to inaccurate interpretation post-concussion, or learning effects. To avoid inaccurate variability in performance that may complicate trainers' decisions, there is a high demand for an objective sideline measure to better determine the outcome of an athletic head injury.
 
The current EYE-TRAC Advance (ETA) study uses a predictive visual tracking paradigm to measure gaze error variability. The addition of EYE-TRAC Advance: Technology Verification (ETA-TV) will help to fill knowledge gaps that exist in the current ETA protocol and contribute to the overall goal of accurately assessing possible impairment following a force to the head.

STUDY DESIGN	This is a prospective multi-center cohort feasibility and exploratory study.
PRIMARY OBJECTIVE	We propose to prospectively study a cohort of 18-25-year-old athletes to establish the reliability of EYE-SYNC data and the utility of the EYE-SYNC goggles as a sideline concussion assessment tool. A clinical research study will be conducted to 1) determine if eye-tracking, assessed on the sideline by EYE-SYNC goggles, is a potential marker of injury that can be used in conjunction with other sideline evaluations to inform decisions regarding removal of athletes from play and 2) to use the EYE-SYNC goggle data as a post- injury recovery curve monitor.
SECONDARY OBJECTIVES	To describe interrelationships among relevant variables used to describe concussion and EYE-SYNC.

NUMBER OF SUBJECTS
	
N = 100 (50 Concussion Subjects, 50 Controls) * Please note that we will continue to consent subjects, until we are able to complete 100 eligible participants for Cohort 2.


SUBJECT SELECTION CRITERIA
	
Inclusion Criteria: Athletes between the age of 18 – 25-years-old. 20/30 or better eyesight (corrected vision allowed). English fluency. CCS - those who experience impact where concussion is highly suspected as evidenced by impairment on any of the SCAT-3 Domains: Symptoms, Immediate Memory, Physical Signs, and Orientation. CTR - a teammate of the CCS who did not experience impact but who was participating in the same sport and session along with the injured teammate at the time of injury.
 
Exclusion Criteria: Clinical diagnosis of a neurological condition including the following: Stroke, Multiple Sclerosis, Epilepsy, Brain Tumor/Cancer, dyslexia, Nystagmus and/or other major neurological condition. Clinical diagnosis of any of the following eye-sight abnormalities: Uncorrected Amblyopia, Uncorrected Myopia, Uncorrected Presbyopia, Uncorrected Farsightedness or Uncorrected Astigmatism. Psychiatric history with any of the following: LIFETIME a. Clinical diagnosis of a Psychotic Disorder, Bipolar Disorder: LIFETIME b. Clinical diagnosis of ADHD or ADD: LIFETIME LAST YEAR c. Clinical diagnosis of Major Depressive Disorder d. Clinical diagnosis of Substance Abuse Disorder within the LAST YEAR. e. Major Anxiety Disorder within the LAST YEAR. MEDICATION g. Use of a psychotropic medication. Cannot have participated previously in any ETA-TV study visits (for instance, a subject that has completed any study visit as a control subject cannot participate as a concussed subject at a later time point)..

INVESTIGATIONAL DEVICE / INTENDED USE
	
The EYE-SYNC[®] portable assessment system consists of two primary components enclosed in a portable aluminum case. The eye tracker is a handheld isolated display environment with embedded eye tracking sensors. The eye tracker is connected to a high-performance Windows tablet through a customized docking station. Included accessories with EYE-SYNC are a U.S. tablet power supply adapter and disposable sanitary masks. Subjects are asked to follow a dot as it moves on the screen.


DURATION OF SUBJECT PARTICIPATION AND DURATION OF STUDY
	
The proposed study will occur within an 18-month window. Active enrollment will continue through the last month of the study or intended sample size is reached.
 
Subject participation begins with enrollment, followed by baseline testing, and follow-up assessments (2 days post-injury, 7 days post-injury (+/- 1 day); and 14 days post-injury (+/- 3 days)). Testing follows consent for all subjects and continues through last

	practice/game in study period. Study windows are only to be used in rare situations. Please discuss with Stanford Principal Investigator/Study Sponsor for approval.
CONCOMITANT MEDICATIONS	No psychotropic medication.
EFFICACY EVALUATIONS	
DEM: The Developmental Eye Movement Test is an evaluation of saccadic eye movements. In this test, the subject reads the numbers presented on a card from left to right and top to bottom as quickly as he/she can without making any errors.
 
ANAM-SRT: The Automated Neuropsychological Assessment Metrics (ANAM) is a computerized neurocognitive assessment tool designed to measure a wide range of cognitive functions. The Simple Reaction Time subtest is used as an index of attention (i.e., reaction time and vigilance) and visuo-motor response timing.
 
SCAT-3: The Sport Concussion Assessment Tool (SCAT) is a widely used sideline concussion assessment tool used to evaluate the presence of neurocognitive impairment following a concussion. In the symptom evaluation, the subject self-reports the presence and severity of 22 concussion-related symptoms on a likert scale from 0-6. The SCAT3 tests the subject's orientation using Maddocks questions, and also includes the administration of the Standardized Assessment of Concussion (SAC). The SAC includes sections that test immediate memory and balance (modified BESS).

PRIMARY ENDPOINT	Our primary endpoint will be the acquisition of sufficient data to establish integrity and reliability of EYE-SYNC data and to compare and characterize trajectories of EYE-SYNC measurements in injured versus non-injured athletes.
SECONDARY ENDPOINTS	Our secondary endpoint will be to characterize interrelationships among variables relevant to concussion including DEM, ANAM-SRT, and SCAT-3 scores with EYE-SYNC.
OTHER EVALUATIONS	History and Demographics
SAFETY EVALUATIONS	N/A – EYE-SYNC is a minimal-risk noninvasive assessment tool, not an invasive assessment or treatment modality.
PLANNED INTERIM ANALYSES	When approximately 50% of subjects have completed the study, an interim analysis for safety will be conducted. Serious adverse events will be monitored by all site Investigators, [name], and the Stanford Concussion and Brain Performance Center (SCBPC) Coordinators on an ongoing basis throughout the study.

STATISTICS
Primary Analysis
Plan and Rationale
for Number of
Subjects

Descriptive Statistics: We will provide descriptive statistics for all subjects included in our study. Specifically, for continuous variables such as age, and scores from DEM, ANAM-SRT, SCAT-3, and EYE-SYNC, we will provide means, medians, standard deviations and interquartile ranges. For categorical variables such as race, ethnicity and previous history of injury, we will present frequency distributions. We will utilize graphical tools such as histograms and box plots to describe distributions of continuous variables. If needed to adhere to modeling assumptions, we may consider transformations of outcomes, such as a log transformation.

Handling of Missing Data: We anticipate minimal missing data in this study. We expect that a small proportion of subjects recruited for the longitudinal study (1%) will not complete all visits. We will fully describe missing data for each variable and any pertinent patterns of missingness (e.g., how missingness is related to specific baseline measurements or time, if at all). The statistical methods we propose are particularly flexible for missing data and allow for systematic missingness that is related to observed features.

Statistical Tools for Each Aim: Our first aim addresses the integrity of data generated by EYE-SYNC. Specifically, in Aim 1A, we will characterize the feasibility of collecting and generating data in real-time as injuries occur by considering the proportion of time we are able to collect 3 subsequent measures using EYE-SYNC on the sideline in the field from a case using data from cases included in *Cohort 2* (described above). We deem EYE-SYNC to be a promising tool to be used on the field if we are able to make use of it 90% of the time. This will be tested using a one-sided exact binomial test. With 50 cases, we have excellent power to evaluate feasibility. More specifically if we use a decision rule such that we conclude EYE-SYNC to be a promising and practical tool to be used in the field if we have complete information on 40 of the 50 cases, we have over 95% power when the true rate of complete data is 90% with a type I error of 0.04 under the null hypothesis that an unacceptable rate of complete data is 70%.

The goal of Aim 2 is to assess whether data from EYE-SYNC correlates with clinically meaningful endpoints. To that end, we will create *Cohort 2* by collecting data (in replicates of 3) at immediately post impact, 2 days from injury, 7 days from injury and 14 days from injury from 50 cases (defined as those who experience impact where concussion is highly suspected) and 50 matched controls (a teammate who did not experience impact but who was participating in the same sport and session along with the injured teammate at the time of injury). Using mixed effects regression techniques, we will examine whether the trajectory of EYE-SYNC changes over time for those injured differs significantly from those who were not injured. In

	
addition, we will characterize trajectories of change in EYE-SYNC over time for those injured and for athletes who are injury free. Such models account for the correlation of scores within a subject over time as well as for the matched pairing of cases and their corresponding teammates. In addition, such models are robust to assumptions regarding missing data.
 
The goal of Aim 3 is to describe interrelationships among relevant variables used to describe concussion and EYE-SYNC. This aim is fairly exploratory but will pave the way for future studies. We will rely on mixed effects techniques to characterize relationships of interest.

--	--

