2.3 Study design

2.3.1 General study design

This is a prospective multi-center cohort feasibility and exploratory study.

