The goal of Aim 2 is to assess whether data from EYE-SYNC correlates with clinically meaningful endpoints. To that end, we will create *Cohort 2* by collecting data (in replicates of 3) Immediately Post Impact, 2 days from injury, 7 days from injury and 14 days from injury from 50 cases (defined as those who experience impact where concussion is highly suspected) and 50 matched controls (a teammate who did not experience impact but who was participating in the same sport and session along with the injured teammate at the time of injury). Using mixed effects regression techniques, we will examine whether the trajectory of EYE-SYNC changes over time for those injured differs significantly from those who were not injured. In addition, we will characterize trajectories of change in EYE-SYNC over time for those injured and for athletes who are injury free. Such models account for the correlation of scores within a subject over time as well as for the matched pairing of cases and their corresponding teammates. In addition, such models are robust to assumptions regarding missing data.

The goal of Aim 3 is to describe interrelationships among relevant variables used to describe concussion and EYE-SYNC. This aim is fairly exploratory but will pave the way for future studies. We will rely on mixed effects techniques to characterize relationships of interest

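### Objective 1 asks whether sideline EYE-SYNC could inform removal from play, but the only injured-versus-uninjured test compares mean trajectories and no analysis measures how well Visit 1 scores separate individuals

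*Combined protocol and SAP*

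**What the plan says.** The synopsis (Primary Objective) speaks of "the utility of the EYE-SYNC goggles as a sideline concussion assessment tool" and then sets, as the first of two purposes, to determine whether eye-tracking at the sideline is a potential injury marker that could serve, alongside other sideline tests, "to inform decisions regarding removal of athletes from play". The second purpose is monitoring of recovery. Section 2.3.1 qualifies the whole study: "This is a prospective multi-center cohort feasibility and exploratory study". The size is "N = 100 (50 Concussion Subjects, 50 Controls", each control being a teammate matched to a case.

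The analyses in the synopsis and in section 3.1.2 are:

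- **Aim 1A:** an exact binomial test of how often three EYE-SYNC measures can be collected, in cases only.
- **Aim 2:** mixed-effects regression, in which "we will examine whether the trajectory of EYE-SYNC changes over time for those injured differs significantly from those who were not injured". It is accompanied by a description: "we will characterize trajectories of change in EYE-SYNC over time for those injured and for athletes who are injury free".
- **Aim 3:** exploratory mixed-effects associations of EYE-SYNC with DEM, ANAM-SRT and SCAT-3.
- **Descriptive statistics:** means, medians, SDs, interquartile ranges, histograms and box plots over all subjects.

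The primary endpoint (section 3.1.1) covers data integrity, reliability and trajectories. Neither the synopsis nor section 3.1.2 plans an AUC, a sensitivity, a specificity, an EYE-SYNC cut-off or a minimum degree of separation.

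**The concern.** Removal from play is decided one athlete at a time, at the sideline. The statistical quantity that bears on it is how far the Visit 1 scores of injured and uninjured athletes overlap. The Aim 2 test addresses something else, in two respects.

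- **It is not tied to Visit 1.** A group-by-time effect can arise from differences at days 2 to 14. Conversely, a gap that stays constant over all four visits produces no group-by-time effect, however large the gap.
- **It concerns means.** With 50 per group, means can differ convincingly while most individual scores overlap.

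At the end of the study, objective 1 would have no planned result that answers it. The trajectory p-value would be the nearest thing to hand, and it could be read as saying more about sideline use than it does.

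**Working it through.** **The plan's own figures.** Aim 2 has no stated alpha, effect size, SD, correlation or power, so there is nothing to reproduce for the analysis in question. The only power statement is for Aim 1A (40 of 50 complete, null 70%, alternative 90%, type I error 0.04, power over 95%). Exact binomial: at least 40 of 50 gives type I error 0.079 and power 0.991; at least 41 of 50 gives 0.040 and 0.975. The stated error therefore fits a threshold of 41. That is a separate matter and does not affect this point.

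**Inputs.** From the documents: n = 50 per group and four visits. Assumed, because the documents do not give them: two-sided 5% level; normal scores with equal SD, set to 1; a Visit 1 gap of d SD decaying over the four visits as d × (1, 0.6, 0.3, 0); within-subject correlation w = 0.3, 0.5 or 0.7 (compound symmetry); no correlation between partners in a pair.

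**Step 1: group-by-time test, 3 df.** The profile has mean 0.475. Deviations from it are 0.525, 0.125, −0.175 and −0.475, and their squares sum to S = 0.5475. The noncentrality is

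λ = (n/2) × d² × S / (1 − w) = 13.69 × d² / (1 − w).

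With 3 and 3 × 98 = 294 df the 5% critical F is 2.635. The observed result is just significant when λ = 3 × 2.635 = 7.906. Power is 80% when λ = 11.05. Hence

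d = √[λ (1 − w) / 13.69].

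**Step 2: convert d to individual separation at Visit 1.** AUC = Φ(d/√2). Sensitivity at 90% specificity = Φ(d − 1.2816).

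| w | Criterion | d at Visit 1 | AUC | Sensitivity at 90% specificity |
|---|---|---|---|---|
| 0.3 | just significant | 0.64 | 0.67 | 26% |
| 0.5 | just significant | 0.54 | 0.65 | 23% |
| 0.7 | just significant | 0.42 | 0.62 | 19% |
| 0.3 | 80% power | 0.75 | 0.70 | 30% |
| 0.5 | 80% power | 0.64 | 0.67 | 26% |
| 0.7 | 80% power | 0.49 | 0.64 | 21% |

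Example, w = 0.3, just significant: d = √(7.906 × 0.7 / 13.69) = 0.636; AUC = Φ(0.450) = 0.67; sensitivity = Φ(−0.646) = 26%.

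**Step 3: can the planned sample estimate an AUC?** Hanley-McNeil, 50 and 50, groups taken as independent: SE² = [A(1 − A) + 49(Q1 − A²) + 49(Q2 − A²)] / 2500, with Q1 = A/(2 − A) and Q2 = 2A²/(1 + A). The 95% half-widths (1.96 × SE) are:

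- A = 0.60: 1.96 × 0.0566 = 0.11
- A = 0.75: 1.96 × 0.0488 = 0.10
- A = 0.90: 1.96 × 0.0321 = 0.06

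An AUC of 0.65 would have an interval of about 0.54 to 0.76, and one of 0.90 about 0.84 to 0.96. The sample can tell a weak marker from a strong one.

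**The case against.** The strongest reply is that the plan claims little. It speaks of a potential marker, used alongside other evaluations, in a feasibility and exploratory study. The specific aims and the primary endpoint contain no diagnostic-accuracy aim, and a group difference is a usual first step for a candidate marker. This stands, and it limits the weight of the point. It does not remove it: the objective is primary and is worded as a determination, and an exploratory study is a natural place to estimate separation.

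A reader might go further and infer that objective 1 will be decided by the Aim 2 p-value. The documents do not say so. They say only that the model will examine whether the injured trajectory "differs significantly from those who were not injured", and nothing links that result to removal from play. The only explicit rule for calling the device promising is the Aim 1A completeness rule.

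A reader might also cite the smaller threshold of a single-visit comparison of means: 0.39 SD with no pair correlation down to 0.28 SD with 0.5 (AUC 0.61 to 0.58). That is not the planned test. Nor can one conclude that the device would miss most concussed athletes in use. The sensitivities above depend on a specificity of 90% that I chose and on stand-alone use, whereas the plan describes use with other evaluations.

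The planned histograms and box plots could reveal overlap if drawn by group at Visit 1. They are not specified that way and carry no interval, so they mitigate the gap without closing it.

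Finally, an AUC from these data would not settle the sideline question. Cases are selected by SCAT-3 impairment and controls had no impact (section 2.4.3), whereas the real decision concerns athletes after a suspected hit. In Figure 2 the footnote requiring immediate sideline EYE-SYNC is attached only to the case column, so measurement conditions may differ too. These objections stand and must be stated beside any AUC.

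**Conclusion.** The point holds as a gap between an objective and its analysis. Objective 1 has no planned measure of individual separation at the sideline, and the one between-group test is neither specific to Visit 1 nor a measure of overlap. Under the assumptions listed, Aim 2 reaches significance at a Visit 1 AUC of about 0.62 to 0.67 and 80% power at 0.64 to 0.70, so a clear result is compatible with weak sideline separation. A different decay pattern, or correlation between partners in their changes over time, would move these figures. Non-normal scores would change the conversion to AUC.

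The documents do not support saying that the trial will declare EYE-SYNC fit for removal decisions on a p-value. I would label this a cheap improvement, not a flaw that invalidates the plan.

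**What to change.** In section 3.1.2 (Aim 2) and the matching synopsis text, add for objective 1:

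- A pre-specified AUC for CCS versus CTR at Visit 1, using one stated summary of the three replicates (for example their mean), with a 95% confidence interval from a bootstrap that resamples matched pairs.
- As supporting description, sensitivity at one specificity fixed in advance, with its interval. This will be less precise than the AUC: even with a known cut-off, 40 of 50 (80%) has an exact 95% interval of 66% to 90%.
- A statement that the trajectory p-value alone will not be taken as support for objective 1.
- A statement that the AUC is probably optimistic, because of how cases and controls were selected, and so supports no more than a potential-marker conclusion.

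Keep the mixed model for the recovery objective.

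The cost is a paragraph of text and a short analysis of measurements already scheduled, with no extra subjects or tests. The downsides are an AUC interval of about ±0.06 to ±0.11 (for AUC 0.90 to 0.60) and a result that may look less favourable than a p-value.

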1.0 PURPOSE OF THE INVESTIGATION

1.1 Name of investigational device

EYE-SYNC[®]

1.2 Intended use of the investigational device

We intend to conduct a clinical trial including 50 Concussion Subjects and 50 Controls to compare trajectories of EYE-SYNC measurements in injured versus non-injured athletes and characterize variables related to concussion in relation to EYE-SYNC data.

1.3 Objectives of the clinical investigation

1.3.1 Primary objectives

Specific Aim I: Establish integrity and reliability of EYE-SYNC data

- Specific Aim 1A: Characterize feasibility of collecting data using EYE-SYNC in real-time on the field.

Specific Aim II: Compare and characterize trajectories of EYE-SYNC measurements in injured versus non-injured athletes.

Specific Aim III: Characterize interrelationships among variables relevant to concussion including DEM, ANAM-SRT and SCAT-3 scores and EYE-SYNC.

1.4 Anticipated duration of the clinical investigation

The proposed study will occur within an 18-month window. Active enrollment will continue through the last month of the study or intended sample size is reached.

2.0 CLINICAL PROTOCOL

2.1 Protocol number and title

ETA-TV_34662: EYE-TRAC Advance: Technology Verification

2.2 Protocol version number and date

Version 1.0, October 26, 2015

Version 2.0 January 26, 2015

Version 2.1 March 17, 2016

Version 2.2 April 4th, 2016

Version 2.3 April 12th, 2016

2.3 Study design

2.3.1 General study design

This is a prospective multi-center cohort feasibility and exploratory study.

2.3.2 Study design schematic

The proposed study will occur within an 18-month window. Subject participation begins with enrollment, followed by baseline testing, and follow-up assessments.

Figure 1. Eighteen-month study plan

[figure not shown]

Figure 2. Sample Individual Subject Study Timeline

Cohort 2		N=50 CCS N=50 CTR Impact Sustained					
Phase	Prior to game	Visit 1		Visit 2		Visit 3	Visit 4
		Post-Concussion Immediate at Sideline – EYE-SYNC, Level of Alertness. Within 3 hrs* – SCAT-3, ANAM-SRT, DEM		Post Concussion 2 days		Post Concussion 7 days** (+/- 1 day) CCS&CTR	Post Concussion 14 days** (+/- 3 days) CCS&CTR
		CCS	CTR	CCS	CTR		
Informed Consent	X						
Inclusion and Exclusion Criteria and demographics			X ²	X ³			
History of injury				X	X		
SCAT-3 Symptom		X ¹	X	X	X	X	X
SCAT-3 Balance, Orientation and Immediate Memory		X ¹	X	X	X	X	X
DEM		X	X	X	X	X	X
ANAM-SRT		X	X	X	X	X	X
Level of Alertness questions ⁴		X ⁵	X	X	X	X	X
EYE-SYNC (3 times consecutively)		X ⁵	X	X	X	X	X

*DEM, SCAT-3, ANAM-SRT must be performed within 3 hours of impact for Concussed subject (CCS) and within 3 hours post competition or practice for the control subject.

** The study window is only to be used for rare situations where the subject is unable to be seen on the exact date they are scheduled to come in. Please notify the site Investigator immediately for approval if subject needs to be seen within the study window that is provided.

1. Those that display impairment on any of the SCAT-3 domains: Symptoms, Immediate Memory, Physical Signs and Orientation will be registered as CCS subject.
2. CTR subjects: Those that meet the inclusion and exclusion criteria under cohort 2 (section 2.4.3 and 2.4.4), was actively participating in the same game along with the CCS subject at the time of injury.
3. During Visit 2, before performing any study procedures CCS subject must meet all the inclusion and exclusion criteria under cohort 2 (section 2.4.3 and 2.4.4). If subject does not meet all the criteria, CCS subject will be a screen failure. If possible, perform CTR study assessment after confirming that CCS is eligible to continue participation on Visit 2.
4. Level of Alertness questions must always be completed before performing the EYE-SYNC
5. EYE-SYNC must be performed at sideline immediately post impact.

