2.4.3 Inclusion criteria

- Athletes between the age of 18-25 years-old
- 20/30 or better eyesight (corrected vision allowed).
- English fluency.
- CCS - those who experience impact where concussion is highly suspected as evidenced by impairment in any of the SCAT-3 Domains: Symptoms, Physical Signs, Immediate Memory and Orientation. An Injured Athlete is concussed if he/she is FAIL on the Physical Signs, Score = 0 on the Orientation or Scoring below the cutoff scores on the Symptom Checklist and/or Immediate memory SCAT-3 domains.
 - Symptoms: Rating of 2 or higher on any of the following items:
 - Headaches
 - Nausea or Vomiting
 - Dizziness
 - Balance Problems
 - Blurred Vision
 - Feeling Slowed Down
 - Feeling like “in a fog”
 - “Don’t feel right”
 - Physical Signs:
 - Balance (Leg Stances): Number of Error(s) on any of the following 7 subtests classifies a subject as concussed.
 - I. Double Leg Stance: At least 3 errors
 - II. Single Leg Stance: At least 3 errors with either dominant or non-dominant foot
 - III. Tandem Stance: At least 3 errors or more.
 - Balance (Tandem Gait): FAIL on at least 2 of 4 trials:
 - I. FAIL per trial: more than 14 seconds to complete a trial

- II. FAIL per trial, if one or more of the following errors are made
 - a) If step off the line;
 - b) Separation between heel and toe
 - c) Touch/grab the examiner or an object
- Orientation: Score = 0 on any of the following 5 items
 - Date: Score = 0 (any date different from current)
 - Month: Score = 0 (any month different from current)
 - Day of the week: Score = 0 (any different from current)
 - Year: Score = 0 (any different from current)
 - Time: Score = 0 AND answer is MORE than + or – 1 hour apart from the correct time.
- Immediate Memory
 - Recall Total Score = less than 13 words recalled.
- CTR - a teammate of the CCS who did not experience impact but who was actively participating in the same sport and session along with the injured teammate at the time of injury

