2.5 Study Procedures

Post-concussion immediate and scheduled follow-up visits

Data Collection:

2.5.1 Visit 1

1. Visit 1 occurs immediately post-impact. The “Immediate” time frame for “post impact” is quantified as taking place as part of the naturalistic evaluation of the athlete suspected of sustaining a concussion. This will likely be immediately after the identification of a “hit” or other event that would lead to an athlete being evaluated for a possible concussion. At Visit 1, Level of Alertness, EYE-SYNC, DEM, ANAM-SRT, and SCAT-3: Symptom reporting, Physical Signs, Orientation, and Immediate Memory will be obtained (the above tests in combination will be referred to as ‘Testing Battery’).
 - a. Post-impact the subject undergoes EYE-SYNC measurement immediately at the sideline. EYE-SYNC to be performed 3 times consecutively.
 - b. Individuals enrolled as a Concussed Subject (CCS) are defined as those who experience impact where concussion is highly suspected as evidenced by impairment on any one of the SCAT-3 domains: Symptoms, Immediate Memory, Physical Signs or Orientation
 - c. For each CCS subject enrolled, immediately enroll a Control Subject (CTR). A CTR subject is defined as a teammate who did not experience impact, but who was actively participating in the same sport and session along with the injured teammate at the time of injury. The CTR subject also receives the Testing Battery. Prior to performing the Testing Battery, ensure the CTR subject meets the Inclusion and Exclusion criteria – Cohort 2 as per section 2.4.3 and 2.4.4.
 - d. CTR subject will complete Demographics during Visit 1.

2.5.2 Visits 2, 3 and 4

1. CCS must meet the inclusion and exclusion criteria prior to performing any assessments on Visit 2 (2 days post-injury). If CCS is ineligible, both CCS and CTR will discontinue participation in the study.
2. History of injury data for CCS and CTR subjects are collected during Visit 2.
3. Following CCS eligibility to continue participation in study, testing battery will be performed by both CCS and CTR.
4. During Visit 3 and Visit 4, all the assessments in the testing battery will be completed both by CCS and CTR.

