3.1.3 Data and Safety Monitoring and Training

The research team will consist of investigators and research assistants familiar with the administration of EYE-SYNC goggles, desktop eye-tracking, and ANAM-SRT. Appropriate personnel will undergo extensive training in the administration of Developmental Eye Movement Test (DEM) and SCAT3 to establish high inter-rater reliability. Additionally, the Stanford will provide Academic Research Organization services (coordination and monitoring), data management and statistical analysis.

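### At Visit 1 EYE-SYNC precedes the SCAT-3 scoring that decides who is a case, and nothing in the plan keeps the EYE-SYNC output from the SCAT-3 rater

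*Combined protocol and SAP*

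**What the plan says.** **Order.** Figure 2 (section 2.3.2) heads the Visit 1 column "Post-Concussion Immediate at Sideline – EYE-SYNC, Level of Alertness. Within 3 hrs* – SCAT-3, ANAM-SRT, DEM", and its footnote 5 states that "EYE-SYNC must be performed at sideline immediately post impact". Section 2.5.1 gives the same sequence. Step a reads "Post-impact the subject undergoes EYE-SYNC measurement immediately at the sideline"; the SCAT-3 definition of a case follows as step b.

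**Case status.** Footnote 1 to Figure 2 says: "Those that display impairment on any of the SCAT-3 domains: Symptoms, Immediate Memory, Physical Signs and Orientation will be registered as CCS subject". Section 2.4.3 gives the cut-offs. One of them is "Single Leg Stance: At least 3 errors with either dominant or non-dominant foot". A tandem-gait trial fails if it takes more than 14 seconds or if the athlete makes a listed error, such as leaving the line or parting heel from toe; two failed trials of four count as impairment. Controls are not selected by SCAT-3. A control is "a teammate of the CCS who did not experience impact but who was actively participating in the same sport and session".

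**Safeguards.** Section 3.1.3 (Data and Safety Monitoring and Training) says: "Appropriate personnel will undergo extensive training in the administration of Developmental Eye Movement Test (DEM) and SCAT3", with good agreement between raters as the aim. No section masks the SCAT-3 rater, assigns separate testers, hides the device output, or has SCAT-3 completed before the output is viewed.

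**Use of the data.** Under section 3.1.2, Aim 2 compares EYE-SYNC trajectories between injured and uninjured athletes with mixed models. Aim 3 relates EYE-SYNC to other measures, SCAT-3 among them. Both tests are done at all four visits.

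**The concern.** EYE-SYNC is the marker under study, and SCAT-3 decides which impacted athletes enter the injured group. If a rater sees the marker before making a judgement call on SCAT-3, the marker can help to choose its own cases. A poor tracing may make a third stance error easier to call in a borderline athlete, and a clean one may make it harder. The case group would then lean towards poor EYE-SYNC values even if the marker carried no information about injury.

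Two results would be exposed: the Aim 2 comparison, because the injured group is selected partly on the outcome, and the Aim 3 association, because one variable influences the scoring of the other. Training for inter-rater agreement does not guard against this, since raters who see the same tracing can agree with each other and share the same bias. Modelling cannot undo it afterwards, because the plan does not record who had seen the reading.

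**Working it through.** The plan gives no figure on this point, so there is none to reproduce. The check has two parts: how far the text supports the mechanism, and an illustration of size on assumed inputs.

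**1. What the text supports**

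- *EYE-SYNC first at Visit 1.* Supported by Figure 2, its footnote 5, and the step order in 2.5.1. The 3 hours for SCAT-3 is a maximum, so the reverse order is not expressly forbidden, but it is not the planned one.
- *SCAT-3 sets case status.* Supported. One impaired domain is enough.
- *Room for judgement.* Partial. Section 2.4.3 also qualifies an athlete by a self-rating of 2 or higher on any of eight symptoms, one wrong orientation item, or fewer than 13 words recalled. These are self-reports or have fixed answers. Judgement enters mainly through stance errors and the tandem-gait error calls. A rater can therefore change case status only for an athlete who passes everything else.
- *Output visible to the rater.* Not stated. Section 4.0 describes an eye tracker connected to a tablet and does not say what is shown, or when.
- *Same person runs both tests.* Not stated.
- *Visits 2 to 4.* The only stated order is that the alertness questions precede EYE-SYNC. SCAT-3 does not set case status there; eligibility is confirmed at Visit 2 before any of that visit's assessments.

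**2. Size, on assumptions that are not in the documents**

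Assume that the output is visible, that EYE-SYNC (standardised, higher = worse) has no true relation to SCAT-3 status, and that a borderline athlete is scored impaired 50% of the time. Suppose that seeing the reading moves this to 70% in the worse half and 30% in the better half.

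- Mean of the upper half of a standard normal: 0.798. Lower half: −0.798.
- Mean among borderline cases: [0.5 × 0.7 × 0.798 − 0.5 × 0.3 × 0.798] / 0.5 = 0.798 × (0.7 − 0.3) = 0.32 SD.
- If borderline athletes are a share *b* of all cases and the rest average zero, the whole case group shifts by 0.32 × *b*. For *b* = 15%: 0.05 SD. For *b* = 50%: 0.16 SD.
- Standard error of a 50 v 50 difference at one visit, ignoring pairing and replicates: √(2/50) = 0.20 SD. The chance of a significant result in the favourable direction is P(Z > 1.96 − shift/0.20), about 4% at 0.05 SD and about 12% at 0.16 SD, against a nominal 2.5%.

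A second set of assumptions shows how far the answer depends on its inputs. Suppose that a share *f* of cases is admitted only because the rater saw a value above a cut *c*, so that the shift is *f* × E[Z | Z > *c*]. For *f* from 5% to 30%, this gives 0.04 to 0.24 SD with *c* at the mean (multiplier 0.798) and 0.08 to 0.46 SD with *c* at +1 SD (multiplier 1.525). The documents give no basis for choosing between these inputs.

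**The case against.** The strongest reply is that the mechanism rests on facts that the documents do not give. A reader might infer from section 3.1.3 that the same staff run EYE-SYNC and SCAT-3. The section says only that the research team is familiar with EYE-SYNC and that suitable personnel are trained in SCAT-3; it does not say who does which. A reader might also infer that a score appears at the sideline and that athletes with good readings will drop out of the case group. Nothing says that a score is displayed, and no EYE-SYNC cut-off appears anywhere. Both objections stand, so the point must stay conditional.

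Three further objections limit its reach, and they also stand. Most routes into the case group leave little to judgement. SCAT-3 is not a reference standard for the whole comparison, because controls are defined by absence of impact and no sensitivity or specificity against SCAT-3 is planned. The order problem belongs to Visit 1 and should not be extended to all four visits.

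On size, the 0.05 to 0.16 SD range comes from invented inputs, lies below one standard error (0.20 SD), and describes a single-visit mean, whereas Aim 2 tests trajectories over four visits. That is fair, and the figure is not an estimate.

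The study is also described as feasibility and exploratory work. This lowers the stakes without removing them: Aim 2 still asks whether the groups differ significantly, and the stated purpose is to judge EYE-SYNC as a possible marker of injury.

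None of this answers the core point. The plan puts the marker before the case-defining test and contains no rule that separates them.

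**Conclusion.** The point holds in a conditional form. At Visit 1 the plan places EYE-SYNC before the SCAT-3 scoring that registers cases, and its only rater safeguard is training. If the output is visible to the rater, it can affect the judgement-based balance items for athletes who pass every other item. From there it can affect who becomes a case (Aim 2) and the EYE-SYNC/SCAT-3 association (Aim 3). Control status is not affected. Nor is Aim 1A, which counts completed recordings and does not use their values.

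The size is unknown. The shift of about 0.05 to 0.16 SD in the Visit 1 case mean assumes a visible output, no true effect, a 50% borderline scoring rate moved to 70/30, and borderline athletes making up 15% to 50% of cases. The upper end is doubtful given how many qualifying items leave no room for judgement. The effect on the trajectory test and on the Aim 3 association has not been calculated.

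The documents do not support the conclusion that this bias will occur, or that the study is invalid because of it. They support the conclusion that the plan leaves it open and that a simple procedure would close it.

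**What to change.** **Visit 1.** Add to section 2.5.1 and Figure 2 that SCAT-3 is scored, and the CCS registration decision entered on the CRF, before the rater sees the EYE-SYNC result. The operator confirms only that three recordings were saved, which is all that Aim 1A needs. Test timing does not change.

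**CRF and analysis.** Record the time of each test and whether the SCAT-3 rater had seen the reading. Repeat the Visit 1 comparison and the Aim 3 association without the athletes whose rater had seen it.

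**Visits 2 to 4.** Score SCAT-3 before the EYE-SYNC result is opened. This protects Aim 3 only.

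**Cost.** A protocol sentence, a few CRF items, a staff instruction and one sensitivity analysis. No extra assessor is needed if the output can stay unopened. The downside is that the EYE-SYNC result is seen later, by up to 3 hours at Visit 1. If the device shows its output automatically, record rater exposure and rely on the sensitivity analysis instead. That is weaker, because it cannot recover athletes who were never registered. If the device already withholds its output at the sideline, saying so in the protocol closes the Visit 1 point.
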